8.4 Baseline and Demographic Characteristics

Descriptive statistics will be used to summarize Subject demographics and baseline characteristics.

8.5 Efficacy Analyses

All effectiveness analyses will be analyzed on the ITT population through the 6-month visit, using descriptive statistics to summarize results separately for treatment and control groups. No comparative inferential statistics will be conducted. In addition, descriptive statistics will summarize percent change in FEV₁ from baseline to 12 and 36 months for all coil treated subjects. Baseline will be defined as the last measurement taken prior to coil treatment.

Descriptive statistics will summarize effectiveness endpoints at 12, 24 and 36 months follow-up.

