SD	Standard Deviation
T	Temperature
TLC	Total Lung Capacity
Tx	Treatment
UADE	Unanticipated Adverse Device Effect
US	United States
USADE	Unanticipated Serious Adverse Device Effect
VC	Vital Capacity

PROTOCOL SYNOPSIS

Reference	BTG-004517-01-FR
Title:	A Randomized Controlled Study of PneumRx Endobronchial Coil System Versus Standard-of-Care Medical Management in the Treatment of Subjects with Severe Emphysema (ELEVATE)
Sponsor:	Boston Scientific Corporation [name]
Timelines and duration:	Study Duration: All Subjects randomized to Treatment will be followed for 36 months post initial treatment. Subjects randomized to Control will be eligible to crossover and receive treatment as soon as possible. Crossover subjects will then be followed for 36 months post initial treatment. Control subjects who choose not to crossover will exit the study immediately. Expected Enrollment Start: Early 2018 Estimated Study Completion: First half 2023
METHOD	
Design:	Prospective, multicenter, open label, randomized (2:1), controlled study comparing outcomes in subjects treated with the PneumRx Endobronchial Coil System (Coil) to a medically-managed control group. The medically-managed control group will be eligible to crossover after 6 months.
Population:	The population studied included severe emphysema patients indicated for Coil treatment per the approved, CE marked Instructions for Use (IFU), who met the following inclusion criteria and did not meet any of the exclusion criteria. Inclusion Criteria: 
 1. Read, understood and signed the Informed Consent form 2. Meets indications for use per the IFU 3. Bilateral heterogeneous and/or homogeneous emphysema 4. 15% predicted \leq Post bronchodilator Forced Expiratory Volume in 1 second (FEV₁) \leq 45% predicted 5. Post bronchodilator Residual Volume (RV) \geq 200% predicted 6. Post bronchodilator Total Lung Capacity (TLC) $>$100% pred. 7. Post bronchodilator RV/TLC $>$55% 8. Dyspnea related to hyperinflation scored \geq 2 on modified Medical Research Council (mMRC) dyspnea scale despite optimal medical management 9. Receiving optimal drug therapy and medical management according to clinical practice. 10. Performing regular physical activity, at least 2 times per week ¹

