1 SCHEDULE OF VISITS

Treatment/Control Group Subjects:

Procedure / Assessment	Baseline	Randomization	Treatment (Tx) 1*	Treatment (Tx) 2 ⁺⁺⁺	12 Month post treatment Follow-Up Visit ⁺⁺⁺	36 Months post treatment Follow-Up Visit ⁺⁺⁺
Informed Consent	X					
Baseline Assessment ¹	X					
Randomization	X	X				
Procedure Treatment	X		X	X		
Medications	X		X	X	X	X
AEs			X	X	X	X
PFTs including Lung volumes and Spirometry	X				X	X
6MWT	X					
QOL (SGRQ, mMRC, CAT, EQ5D)	X					
HRCT (inspiratory and Expiratory)	X				X	X
Chest X-Ray	X		X ²	X ²		
Pregnancy test	X		X	X		

¹Includes demographics, medical history, physical exam, vitals, echocardiogram, and additional pre -treatment evaluations (e.g. blood panel, blood gas).

²At procedure visits, a Chest X-Ray or a still fluoroscopic image will be performed immediately post procedure. A second chest X-Ray should be done before discharge, a minimum of 4 hours following the first chest X-Ray.

*No more than 45 days post baseline visit

⁺⁺⁺ 2 months ±4 weeks post initial coil treatment

⁺⁺⁺ ±4 week

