3.2 Trial Design

This is a prospective, multicenter, open label, randomized (2:1), controlled study comparing outcomes in subjects treated with the Coil System (Treatment) to a medically-managed control group (Control). Control group patients will be eligible for treatment with Coils (Crossover) 6 months after entry into the study.

The study is anticipated to begin enrollment early 2018. All subjects randomized to Treatment will be followed for 36 months post initial treatment. Subjects randomized to Control will be eligible for crossover as soon as possible. Crossover subjects will then be followed for 36 months post initial treatment. The anticipated last patient visit is expected in first half of 2023. If Control subjects choose not to crossover to treatment, they will exit the study immediately.

The data in this study, including Subject characteristics, outcome measures (e.g., health-related QOL, pulmonary function, exercise capacity), and safety (SAEs and specific respiratory AEs of interest), will be collected via the use of an electronic data capture (EDC) system on electronic Case Report Forms (eCRFs).

No biological samples will be taken other than blood draws taken at screening, and no biological samples will be stored for the study.

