3.4 Primary Endpoint (s)

The Co-Primary Effectiveness Endpoint for the study is:

- Percent change in FEV₁ from baseline to 6 months
- Change in St. George's Respiratory Questionnaire (SGRQ) from baseline to 6 months.

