6.2 Pulmonary Function Central Laboratory

A PFT Core lab will provide oversight of PFT tests. This will include training of sites, certification of assessors and review of Baseline and 6 month PFT data to ensure valid measurements meeting the standards defined by ATS/ERS (Miller et al., 2005; Wagner et al., 2005; McIntyre et al., 2005, Miller et al., 2005).

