8.2 Statistical Analysis

The statistical analysis plan (SAP) will be a separate document and will be updated as required, in association with any protocol amendments. The plan will include detailed descriptions of analysis methods, tables, listings and figures and will describe statistical programming considerations.

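### A randomized 2:1 controlled study is planned without any between-group estimate or interval for either co-primary endpoint, and no reason is given

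*Combined protocol and SAP*

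**What the plan says.** The Design row of the synopsis calls this a randomized (2:1), open-label, "controlled study comparing outcomes in subjects treated with the PneumRx Endobronchial Coil System (Coil) to a medically-managed control group". Section 3.2 says nearly the same. Section 3.1.1 sets the objective as prospective confirmation of safety and effectiveness.

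Section 3.4 names two co-primary effectiveness endpoints: percent change in FEV1 over 6 months, and change in the "Respiratory Questionnaire (SGRQ) from baseline to 6 months".

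Section 8.5 covers all effectiveness analyses. They are to be done on the ITT population through the 6-month visit, "using descriptive statistics to summarize results separately for treatment and control groups", and then: "No comparative inferential statistics will be conducted". The Statistical Analyses row of the synopsis says the same for the co-primary endpoint. Section 8.1, despite its title, gives only the randomized counts: 120 in total, 80 Treatment and 40 Control.

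Section 8.2 adds: "The statistical analysis plan (SAP) will be a separate document". That document was not among those supplied.

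**The concern.** The control arm exists to supply a contrast. A change from baseline within the Coil arm mixes any device effect with disease course, regression to the mean and optimized medical care. Only the difference from the randomized control group separates them. The protocol text plans neither that difference nor an interval for it, and does not say why.

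At stake is how both co-primary endpoints are read. Two sets of arm summaries side by side will be compared whatever the protocol says. Without a labelled estimate, readers make that comparison with no stated baseline adjustment, no stated analysis set for the contrast and no visible measure of imprecision. An interval needs no power claim and no success criterion, so the lack of a sample-size justification is no reason to leave it out.

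**Working it through.** **Is a between-group estimate planned anywhere in the protocol?**

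- Synopsis (Statistical Analyses) and Section 8.5: per-arm descriptive summaries, with comparative inference barred.
- Section 8.1: counts only. There is no alpha, power, effect size, SD or margin.
- Section 8.2: methods are left to the separate SAP.
- Abbreviation list: CI is listed, but no analysis section uses it.

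No section plans a difference, interval, model or test for either co-primary endpoint. The bar covers inferential statistics. A purely descriptive difference is not forbidden, but none is planned.

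**The plan's own figure.** 120 × 2/3 = 80 and 120 × 1/3 = 40, which agrees with the stated split. There is no power calculation to reproduce.

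**What precision would the randomized numbers give?** For an unadjusted difference in means with a two-sided 95% interval (the 95% level is my assumption):

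half-width in SD units = t(0.975, n1 + n2 − 2) × √(1/n1 + 1/n2)

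- Complete data, 80 and 40: 1.9803 × √(1/80 + 1/40) = 1.9803 × 0.1936 = 0.3835 SD.
- Assumed 30% missing in both arms, 56 and 28: 1.9893 × √(1/56 + 1/28) = 1.9893 × 0.2315 = 0.4604 SD.

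The documents give no SD, so these illustrations use assumed ranges:

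| Endpoint | Assumed SD (points) | Half-width at 80/40 | Half-width at 56/28 |
|---|---|---|---|
| Percent change in FEV1 | 15 to 25 | 5.8 to 9.6 | 6.9 to 11.5 |
| Change in SGRQ | 10 to 16 | 3.8 to 6.1 | 4.6 to 7.4 |

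Each entry is 0.3835 or 0.4604 times the SD. Baseline adjustment could narrow these intervals, but the documents give no correlation from which to say by how much.

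**Would the data exist?**

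- Section 3.4 and Section 8.5 require 6-month values.
- The Schedule of Visits has no 6-month column, and its row for "QOL (SGRQ, mMRC, CAT, EQ5D" and related instruments is marked at baseline only.
- Section 6.4.3 places follow-up visits at 12 and 36 months after first Coil treatment.
- Section 6.2 refers to core-laboratory "review of Baseline and 6 month PFT data", which concerns lung function and not SGRQ.
- Crossover is at 6 months in the synopsis Design row and in one sentence of Section 3.2. It is as soon as possible in another sentence of Section 3.2 and in Section 4.3, and immediate in Section 5.1.4.

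A 6-month contrast is well defined only once these places agree.

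**The case against.** The strongest reply is that the restriction is deliberate. It appears twice and consistently, and the protocol makes no hypothesis, alpha, margin or power claim. Side-by-side arm summaries can be called comparing outcomes, so there is no strict contradiction. That much stands: a sponsor may choose a descriptive study. What does not stand is leaving the choice unexplained beside comparative wording and a confirmatory objective.

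A reader might infer that the contrast could never be known under this plan. The documents do not support that. If n, mean and SD are reported for each arm, the unadjusted difference and its interval follow by arithmetic. What is lost is a specified, labelled and baseline-adjusted estimate.

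A reader might also infer that missing 6-month values have no rule. The SAP was not seen and may contain one, so this cannot be established.

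A third inference would be that controls are lost selectively, or are treated early and so dilute the difference. Neither is shown. The current schedule omits a 6-month visit for both arms, and two places put crossover at 6 months, in which case dilution could be zero. Full dilution would also require early-treated controls to have the whole effect by then, although Section 5.1.2 describes two procedures about 2 months apart.

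Finally, randomization is reported as complete, so anything added now is post hoc. That stands and limits the weight of the estimate.

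**Conclusion.** The point holds for the protocol text. No between-group estimate or interval is planned for either co-primary endpoint, and no reason is given. The unseen SAP could add a descriptive difference without conflict, but a between-group confidence interval there would contradict both Section 8.5 and the synopsis.

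Sample size does not force the omission. The half-width would be about 0.38 SD with complete data and about 0.46 SD with an assumed 30% missing in each arm. In endpoint units the size rests entirely on assumed SDs. These figures show the precision available; they do not measure harm done.

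This is an inexpensive improvement that should be made. It does not show that the trial is uninterpretable. It is also secondary to the unresolved question of whether 6-month FEV1 and SGRQ data exist. An interval would not remove open-label bias, particularly in a questionnaire score.

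**What to change.** First reconcile the 6-month endpoint (Section 3.4), the visit schedule (Sections 1, 6.2 and 6.4.3) and the crossover timing (synopsis, Sections 3.2, 4.3 and 5.1.4).

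Then, in Section 8.5 and the synopsis, amend both the sentence that confines the analysis to separate arm summaries and the sentence that bars comparison. Changing only the second would leave the first in conflict with the new text. Suggested wording:

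> Results will be summarized descriptively by randomized group. In addition, for each co-primary endpoint the Treatment minus Control difference in mean change from baseline to 6 months (percent change for FEV1) will be reported with a two-sided 95% CI, by randomized group, in ITT subjects with 6-month data, adjusted for the pre-randomization baseline value. This is estimation only; no hypothesis test or success claim will be made.

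Also:

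1. State that the pre-Coil baseline definition in Section 8.5 applies only to the 12- and 36-month summaries of coil-treated subjects. An untreated control has no Coil procedure to anchor it.
2. Report the number with 6-month data in each arm and the number of controls treated before 6 months.
3. Label the analysis as added after randomization (Sections 3.3 and 8.1 report it as done).

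The cost is wording plus one model per endpoint, if the data exist. The interval may be wide, and it is post hoc in an open-label trial.

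If the sponsor keeps the ban, Section 8.5 should give the reason, and the synopsis and Section 3.2 should call the study descriptive. That costs wording only.

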4.3 Subject Crossover

Control group Subjects will be eligible for crossover to Treatment as soon as possible. Control subjects will be eligible for crossover if they still meet all inclusion and exclusion criteria, and if the patient is deemed to benefit from the Coil treatment by the investigator, based on best medical judgment. Crossover subjects will continue in the study through 36 months from first Coil implant. If Control subjects do not crossover to treatment, they will exit the study immediately.

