5.1.4 Duration of Treatment and Follow up

All Subjects randomized to Treatment will be followed for 36 months post initial treatment. Subjects randomized to Control will be allowed immediate treatment and will be followed for 36 months post initial treatment. If Control Subjects do not crossover to treatment, they will exit the study immediately.

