6.4.1 Baseline Visit

After the Subject provides informed consent, the Subject will be evaluated to ensure they are appropriate candidates for use of the Coil System. Eligibility to enroll in the study is assessed as described in Section 4.2.

The following evaluations will be performed as part of the Baseline visit.

- Informed Consent
- Demographic Information
- Medical history information, including comorbidities, smoking status, previous treatments of emphysema and baseline characteristics, physical activity, rehabilitation status
- Medications
- Pulmonary Function Test (PFT)
- Six Minute Walk Test (6MWT)
- Modified Medical Research Council mMRC dyspnea scale will be completed.
- QoL assessments: SGRQ, CAT, and EQ5D will be completed
- Blood gas, including CoHB for smoking cessation confirmation
- Blood test including cardiac panel with BNP test and other biomarker, if available
- Pregnancy test for females of child-bearing potential prior to radiographic procedures
- Echocardiogram
- Vital signs
- Inspiratory and expiratory HRCT (Note: a HRCT scan (inspiratory and expiratory) performed within 6 months prior to baseline may be used if it was acquired per the PneumRx QCT service protocol.)
- Chest X-Ray.

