8.3 Analysis Populations and Sub-Groups

Intent to Treat Population (ITT) – All randomized Subjects, regardless of whether or not treatment was attempted.

Per Protocol Population (PP) - All randomized Subjects without major protocol deviations (see Section 10.9).

Safety Population - All randomized Subjects who enter the bronchoscopy suite for the initial Coil procedure.

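### Does the pre-coil baseline rule in section 8.5 spoil the Control group's 6-month change?

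*Combined protocol and SAP*

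**What the plan says.** Section 8.5 describes two sets of effectiveness summaries. The first is on the ITT population through month 6, "using descriptive statistics to summarize results separately for treatment and control groups", with no inferential comparison. The second is percent change in FEV1 at 12 and 36 months in everyone who received coils, whichever arm they started in. The next sentence reads: "Baseline will be defined as the last measurement taken prior to coil treatment". It names no arm, endpoint or time point, and no other section of the supplied document gives an analysis definition of baseline.

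These sections bear on how to read it:

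- Section 3.4 states both co-primary endpoints as changes between baseline and month 6.
- Section 8.3 defines ITT as "All randomized Subjects, regardless of whether or not treatment was attempted", so controls who never receive coils are included.
- Section 6.4.1 describes a Baseline Visit with lung function testing and, for quality of life, "QoL assessments: SGRQ, CAT, and EQ5D will be completed". The visit tables in section 5.1.3 place that visit ahead of randomization in both arms.
- Section 6.2 has the core laboratory review lung function data from Baseline and month 6.
- On crossover, section 3.2 says "Control group patients will be eligible for treatment with Coils (Crossover) 6 months after entry into the study", section 4.3 says "Control subjects will be eligible for crossover if they still meet all inclusion and exclusion criteria", and section 5.1.4 says "Subjects randomized to Control will be allowed immediate treatment".
- Section 8.2 leaves detailed methods to a separate SAP, whose text is not in the supplied document.

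**The concern.** The rule is tied to an event that a control has not had by month 6 if crossover waits until then, and never has without crossing over. Taken at face value for the 6-month summaries, it could set the reference at or after the endpoint, or leave no reference at all. Treated subjects in the Treatment arm would be unaffected, so the distortion would fall almost wholly on one side.

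Because the plan only describes each arm, readers will set the Treatment change beside the Control change. A Control change that is zero by construction would make medically managed patients look stable whatever had happened to them. Two analysts who settled on different baselines would report different Control results on both co-primary endpoints.

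**Working it through.** **Allocation.** 120 × 2/3 = 80 and 120 × 1/3 = 40, as section 8.1 states. The document gives no effect size, SD or crossover rate, so the rest is a comparison of two readings.

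**Notation.** x0 is the Baseline Visit value, x6 the 6-month value, xr a value repeated after month 6 but before coils, and b the analysis baseline. FEV1 change is 100 × (x6 − b)/b. SGRQ change is x6 − b.

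**Wide reading: the rule also governs the 6-month summaries.**

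| Subject | b | Result |
|---|---|---|
| Treatment, coils given | x0 | As intended: first coils are due within 45 days of the Baseline Visit, with no test scheduled between |
| Treatment, never given coils | none | Undefined |
| Control, crosses over after month 6, no repeat test | x6 | x6 − x6 = 0 |
| Control, crosses over after month 6, test repeated | xr | x6 against a later value |
| Control, crosses over before month 6 | x0 or a later pre-coil value | Reference precedes the endpoint, though x6 then follows coils |
| Control, never crosses over | none | Undefined |

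Only the total of 40 controls is known. The number in each Control row cannot be derived.

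**Size if the wide reading were used (assumed values).** Let d be the true mean Control change and f the fraction of controls whose last pre-coil value is x6. If the others keep x0, the displayed mean is (1 − f) × d. For d = −5%:

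- f = 50%: 0.50 × (−5) = −2.5%
- f = 75%: 0.25 × (−5) = −1.25%
- f = 100%: 0 × (−5) = 0%

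For d = −2% the same fractions give −1.0%, −0.5% and 0%. The error is f × |d| and cannot exceed |d|.

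**SGRQ.** The schedule in section 1 lists SGRQ only at Baseline and has no 6-month or pre-crossover column. If the schedule is complete, the last scheduled pre-coil SGRQ is x0, and b = x0 even under the wide reading. If an unlisted 6-month test is assumed, the schedule's silence cannot prove that nothing was repeated before crossover. So a zero SGRQ change does not follow from the schedule.

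**Narrow reading: the rule governs only the coil-treated summaries.** At 12 and 36 months after coils, b = x0 for the Treatment arm. For a crossover subject, b is the latest value before coils, which is the right reference because the enrolment value may be months old by then. This gives the sentence a clear purpose. The 6-month summaries then use x0 in both arms, and the change is measured from x0 to x6 for each subject with both values.

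**Which reading fits.** A change between baseline and month 6 (section 3.4) needs a baseline that comes before month 6. The wide reading breaks this in two of the four Control rows and supplies no baseline in a third. The narrow reading breaks it in none. Section 6.2 pairs the same two visits, and x0 is collected for both endpoints in both arms.

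**The case for a change.** The strongest case for acting is that this is the only analysis definition of a word used in both co-primary endpoints, and that it has no stated scope. Even on the narrow reading, the 6-month baseline has to be inferred. The SAP cannot be checked, and two sentences would settle the matter with no new data.

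The first two points are true, and so is the algebra for controls who cross over after month 6. But the inference takes little effort. There is one visit named Baseline, it precedes randomization, and it measures both endpoints. Sections 8.2 and 9 send the analyst to the SAP for methods, so section 8.5 is not what a programmer would work from alone. The Control summary is also not the only context for the Treatment change: section 3.1.1 sets the results beside earlier randomized trials. Finally, a block of exact zeros or missing baselines would be obvious in the first output.

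The statements on when controls may cross over (section 3.2 against sections 4.3 and 5.1.4) do conflict and must be reconciled. That is a separate matter, because a Baseline Visit reference for the 6-month summaries does not depend on it.

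**Conclusion.** No change to the plan follows. The scope of the rule is left unstated, but its position and the sections on endpoints, visits and core laboratory review all lead to the same analysis: the Baseline Visit value for the 6-month summaries in both arms, and the last pre-coil value for later summaries of coil-treated subjects. Writing this down would record what is already implied and would alter no result.

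On that reading the effect is nil. On the strained reading it would be a shift of at most the true Control change, plus some missing values, in a descriptive summary with no test attached. The conclusion assumes that the unseen SAP does not extend the pre-coil rule to the 6-month Control summary; nothing in the supplied document suggests that it does.
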